8.2.6. Prohibition of treatment resumption

Study treatment must not be resumed in subjects who are once withdrawn from this study for a reason associated with hepatic function test, QTc, treatment-related serious adverse event, pregnancy, or commencement of a prohibited medication or therapy.

8.3. Lost to follow up

A participant will be considered lost to follow-up if he or she repeatedly fails to return for scheduled visits and is unable to be contacted by the study site.

The following actions must be taken if a participant fails to return to the clinic for a required study visit:

- The site must attempt to contact the participant and reschedule the missed visit as soon as possible and counsel the participant on the importance of maintaining the assigned visit schedule and ascertain whether or not the participant wishes to and/or should continue in the study.
- Before a participant is deemed lost to follow up, the investigator or designee must make every effort to regain contact with the participant (where possible, 3 telephone calls and, if necessary, a certified letter to the participant's last known mailing address or local equivalent methods). These contact attempts should be documented in the participant's medical record.
- Should the participant continue to be unreachable, he/she will be considered to have withdrawn from the study with a primary reason of lost to follow-up.

9. STUDY ASSESSMENTS AND PROCEDURES

- Study procedures and their timing are summarized in the SoA.
- Protocol waivers or exemptions are not allowed.
- Immediate safety concerns should be discussed with the sponsor immediately upon occurrence or awareness to determine if the participant should continue or discontinue study treatment.
- Adherence to the study design requirements, including those specified in the SoA, is essential and required for study conduct.
- All screening evaluations must be completed and reviewed to confirm that potential participants meet all eligibility criteria. The investigator will maintain a screening log to record details of all participants screened and to confirm eligibility or record reasons for screening failure, as applicable.
- Procedures conducted as part of the participant's routine clinical management (eg, blood count) and obtained before signing of ICF may be utilized for screening or baseline purposes provided the procedure met the protocol-specified criteria and was performed within the time frame defined in the SoA.

9.1. Efficacy assessments

9.1.1. Evaluation methods

9.1.1.1. Modified Ashworth Scale (MAS)

According to "2. SCHEDULE OF ACTIVITIES (SoA)" the investigator will use MAS (Table 5) to evaluate the level of spasticity. MAS should be measured and evaluated by the investigator, physiotherapist, or occupational therapist who has been given the training as an assessor.

The test should be performed on sitting position throughout the study. The affected parts should be extended as fast as possible to grade the flexor muscle tones. The final assessment will be made by the investigator in consideration of the information from physiotherapist or occupational therapist. The assessor should in principle remain unchanged throughout the study period.

Table 5 Modified Ashworth Scale (MAS)

0	No increase in muscle tone
1	Slight increase in muscle tone, manifested by a catch and release or by minimal resistance at the end of the range of motion when the affected part(s) is moved in flexion or extension
1+	Slight increase in muscle tone, manifested by a catch, followed by minimal resistance throughout the remainder (less than half) of the ROM (range of movement)
2	More marked increase in muscle tone through most of the ROM, but affected part(s) easily moved
3	Considerable increase in muscle tone passive, movement difficult
4	Affected part(s) rigid in flexion or extension

- MAS measurement as inclusion criteria (Screening and Day 1)

The subject's wrist or fingers and elbow should all be evaluated as inclusion criteria. Subjects meeting the eligibility and randomized should be evaluated for MAS at Visit 1 of Treatment Period 1 on the same day; provided that measurement may be performed only once if the affected part to be evaluated is the same. The detail of inclusion criteria are shown in 6.1.

- MAS measurement during the blinded period

The subject's wrist, fingers, thumb and elbow should all be evaluated during the blinded period. Likewise, the subject's wrist, fingers, thumb and elbow should all be evaluated for MAS at Visit 5 and QRV of the blinded period. Subjects meeting the eligibility and transferred to the open-label period should be evaluated for MAS at Visit 1 of Treatment Period 2 on the same day; provided that measurement may be performed only once if the affected part to be evaluated is the same. Meanwhile, MAS needs to be evaluated again if the affected part to be evaluated is not the same. In subjects who have received no injection to any muscles affecting the thumb, MAS measurement on the thumb will not be performed.

- MAS measurement during the open-label period

During the open-label period, MAS should be evaluated for the flexors at which the muscle given the study treatment functions (fingers, thumb, wrist, elbow, fore-arm) (Table 6). If the subject is determined to be eligible, the V5/QRV and V1 would be on the same day, and therefore, the MAS

measured at V5/QRV of the previous treatment period should not be measured again on V1; the measurement on V5/QRV should be used for the assessment (Figure 6). MAS on flexors to be newly assessed on V1 should be evaluated before dose on V1. The MAS on the shoulder should be evaluated comprehensively for the adductor and invertor.

Table 6 Regions to be evaluated for MAS during the open-label period

Number	Muscles to be injected	Regions to be evaluated for MAS
A1	Biceps brachii	Elbow flexors (flexion)
A2	Brachialis	
A3	Brachioradialis	
B1	Flexor carpi radialis	Wrist flexors (flexion)
B2	Flexor carpi ulnaris	
C1	Flexor digitorum profundus	Fingers (flexion)
C2	Flexor digitorum superficialis	
C3	Lumbricales interossei	
D1	Flexor pollicis longus	Thumb (flexion, adduction)
D2	Adductor pollicis	
D3	Opponens pollicis	
E1	Pronator teres	Forearm (pronate)
E2	Pronator quadratus	
F1	Teres major	Shoulder (flexion, adduction, and internal rotation)
F2	Latissimus dorsi	
F3	Pectoralis major	
F4	Subscapularis	

Visit	SV	Part 1					Part 2					Part 3					Part 4					
		V1	V2	V3	V4	V5	V1	V2	V3	V4	V5	V1	V2	V3	V4	V5	V1	V2	V3	V4	V5	
A.Elbow	●	●	●	●	●	●	(○)	●	●	●	●	(○)	●	●	●	●	(○)	●	●	●	●	
B.Wrist	●	●	●	●	●	●							●	●	●	●	●	(○)	●	●	●	●
C.Finger	●	●	●	●	●	●	(○)	●	●	●	●	(○)	●	●	●	●	(○)	●	●	●	●	
D.Thumb		●	●	●	●	●																
E.Forearm							●	●	●	●	●	(○)	●	●	●	●	(○)	●	●	●	●	
F.Shoulder							●	●	●	●	●						●	●	●	●	●	

● : MAS measurement (before treatment)
 (○) : Use V5 or QRV MAS measurement

Figure 6 Subjects to be evaluated for MAS

9.1.1.2. Numeric Rating Scale (NRS)

According to "2. SCHEDULE OF ACTIVITIES (SoA)" the investigator (or subinvestigator) will use NRS (Figure 7) to evaluate the severity of flexors pain.

The investigator will perform the interview on NRS following the assessment of MAS. Each subject will be interviewed on the severity of pain on the treated part when extended based on a scale with 0

being "no pain" and 10 being "the worst imaginable pain"; 1 response on the scale should be selected by the subject.

0	1	2	3	4	5	6	7	8	9	10
No pain										Pain as bad as you can imagine

Figure 7 Numeric Rating Scale (NRS) for pain

- NRS measurement during the blinded period

During the blinded period, the severity of pain in the elbow flexors will be evaluated.

- NRS measurement during the open-label period

During the open-label period, a major part with pain [specify 1 part from among fingers, thumb, wrist, elbow, fore-arm (pronate), and shoulder] will be evaluated for the severity of pain on Visit 1. The part to be evaluated does not have to be the same within each treatment period, but should be the same part as that evaluated for MAS.

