4. OBJECTIVES AND ENDPOINTS

Objectives	Endpoint(s)
Primary	
To evaluate the efficacy of injection of 400 units of the product at Week 6 (finger/ wrist flexors: 240 units, elbow flexors: 160 units), comparing to that of 240 units (finger/ wrist flexors: 240 units, elbow flexors: placebo).	The rate of the subjects that Modified Ashworth Scale (MAS) score was reduced at least 1 from baseline in the elbow flexors (the responder rate).
Secondary	
To evaluate the efficacy of 400 units of the product, comparing to 240 units of the product.	
 • The responder rate of MAS score from baseline in finger, thumb and wrist flexors • Changes in MAS score from baseline in finger, thumb, wrist, elbow, pronation of forearms and shoulder flexors • Changes in Disability Assessment Scale (DAS) from baseline
To evaluate the safety and tolerability of the product of 400 units, comparing to 240 units of the product/ To evaluate the safety and tolerability of 400 units of the product.	
 • Adverse events • Physical examinations • Clinical laboratory tests (haematology, blood biochemistry, urinalysis) • Vital signs (heart rate, blood pressure, body temperature)
Exploratory	
To evaluate the efficacy of 400 units of the product	
 • Changes in MAS score from baseline in finger, thumb, wrist, elbow, pronation of the forearm and shoulder flexors
To evaluate the other efficacy of the product of 400 units, comparing to 240 units of the product/ To evaluate the other efficacy of 400 units of the product	
 • Changes in Numeric Rating Scale (NRS) for pain from baseline • Changes in other items of DAS from baseline • Clinical Global Impression of Change (CGI) of functional disability by an investigator • CGI of functional disability by a patient • Time to patient-reported onset of spasticity symptom relief • Patient-reported benefit of injection • Time to qualification for retreatment
To evaluate neutralizing antibody production	
 • Testing for neutralizing antibody

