5. STUDY DESIGN

5.1. Overall Design

This study is a 48-week multicenter, phase III study (a placebo controlled, randomized, double-blind comparative study and an open-label, uncontrolled study) to evaluate the efficacy and safety of the product in patients with post-stroke upper limb spasticity. The study period is up to 52 weeks, consisting of a screening phase up to 4 weeks, minimum 12-week blind phase (Part 1), maximum 36-week open-label phase (12 weeks per cycle with maximum 3 treatment periods, Part 2, Part 3 and Part 4). (Figure 5).

[figure not shown]

Figure 5 Study Design

In this study, the efficacy of 400 units of the product at Week 6 is evaluated, comparing to that of 240 units, and improvement tendencies are also evaluated in patients with post-stroke upper limb spasticity. The improvement will be defined as at least 1 reduction on the MAS score from baseline (a measurement value before injection of Day 1). The responder rate (the rate of the subjects that MAS score is reduced at least 1 from baseline) in the elbow flexors at Week 6 is set as an endpoint. As a point estimate, if the responder rate in the 400 units group outweighs that in the 240 units group, improvements tendencies will be considered to be positive.

For injection, use of the following any one of the tools: EMG, electrical stimulator, or ultrasonography, is recommended to ensure identification of the exact injection site. In the blind phase, use of at least one of the following tools: EMG, electrical stimulator, or ultrasonography, will be essential to ensure identification of the muscle to be injected correctly.

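### The open-label pain NRS may be rated on a different body part at different visits of one treatment period, so its change from baseline need not describe pain in any one part

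*Protocol*

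**What the plan says.** In the current (Amendment 2) text, Protocol section 9.1.1.2 treats the two phases differently.

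- **Blinded phase.** The part is fixed: "During the blinded period, the severity of pain in the elbow flexors will be evaluated".
- **Open-label phase, choice of part.** "During the open-label period, a major part with pain [specify 1 part from among fingers, thumb, wrist, elbow, fore-arm (pronate), and shoulder] will be evaluated", with Visit 1 given as the occasion.
- **Open-label phase, constancy.** "The part to be evaluated does not have to be the same within each treatment period".
- **Open-label phase, limit on the choice.** The sentence continues: "but should be the same part as that evaluated for MAS".

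The endpoint built on these ratings is exploratory: "Changes in Numeric Rating Scale (NRS) for pain from baseline" (section 4). The schedule of activities (section 2, Table 1) collects the NRS at V1 to V5 and at any retreatment qualification visit (QRV) of each open-label period. Each period therefore has one starting score and several later ones.

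**The concern.** A change score has meaning only if the two scores measure the same thing. The NRS here is pain in one named part on extension. If the part can differ between Visit 1 and a later visit of the same period, the subtraction mixes any change in pain with the difference in pain between two joints.

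What is at stake is the interpretation of the open-label pain results after repeated 400-unit injections. That phase has no concurrent control, so no comparison group would reveal or cancel the error. An analysis plan cannot repair it either: if the Visit 1 part was not rated at Week 6, that score does not exist.

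**Working it through.** The protocol states no figure on this point, so there is none to reproduce. The check is a reading of the relevant sections together, followed by a decomposition of the change score.

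**Step 1. Does any other rule hold the part fixed?**

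- The only limit in section 9.1.1.2 is that the part be one rated for the MAS.
- Section 9.1.1.1 says which parts those are: "During the open-label period, MAS should be evaluated for the flexors at which the muscle given the study treatment functions". Every region whose muscles were injected is rated.
- Sections 5.1.3 and 7.1 divide 400 units among muscles chosen by the investigator. Adding the upper reference doses in Table 3 by region gives: elbow 200 + 75 + 75 = 350; wrist 100 + 50 = 150; fingers 100 + 75 + 50 = 225; thumb 25 + 25 + 25 = 75; forearm 75 + 50 = 125; shoulder 75 + 150 + 150 + 75 = 450. Within those ranges only the shoulder could take the full 400 units alone. In any other case at least two regions are injected, rated for the MAS, and so open to the NRS.
- The limit therefore narrows the candidates without naming one from V1 to V5. No other sentence in the protocol requires the same NRS part at the start and at follow-up of an open-label period.

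**Step 2. How does the protocol treat comparable measures?**

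| Measure | Is the object of the rating held fixed? |
|---|---|
| NRS, blinded phase (9.1.1.2) | Yes, elbow |
| DAS main item (9.1.1.3) | Yes, for the whole study |
| NRS, open-label phase (9.1.1.2) | No, expressly not required within a period |

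The open-label NRS is the exception.

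**Step 3. What does a switch do to the score?**

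Let A be the part rated at Visit 1 and B the part rated at Week 6 of the same period.

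Recorded change = B(Week 6) − A(Visit 1)
= [A(Week 6) − A(Visit 1)] + [B(Week 6) − A(Week 6)]

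The first bracket is the change wanted. The second is the error. If a share *s* of subjects switch, the mean change is shifted by *s* × the mean error among switchers. The documents give neither quantity.

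**Step 4. Is the sign determined?** No. Two illustrations, all values assumed, each with *s* = 20%:

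- A stays at 6 and the rating moves to a milder part at 3. Error = 3 − 6 = −3. Shift = 0.20 × (−3) = −0.6, a false fall in pain.
- A falls from 6 to 3, and the rating moves to the part that is now worse, at 5. True change = 3 − 6 = −3; recorded change = 5 − 6 = −1; error = 5 − 3 = +2. Shift = 0.20 × 2 = +0.4, which hides part of a real fall.

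Under these assumptions the shift runs from −0.6 to +0.4 points on the 0 to 10 scale, and it is zero if nobody switches. The figures show only that the sign is open; they do not estimate the effect.

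**The case against.** The strongest reply is that this is a wording slip. Naming the part at Visit 1 has little purpose if it may change at the next visit, and the injected muscles may differ from one open-label injection to the next. On that view the authors meant that the part may differ between treatment periods. This is plausible, and it is a reason not to call the rule a deliberate design decision. It does not remove the problem: sites follow the written sentence, which says the reverse, and the same sentence stands in all three protocol versions in the file.

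A second reply is that the SAP can settle the details. That holds for the definition of baseline and for the summary tables. It does not hold for which joint is rated at each visit, which is a data-collection rule.

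A third reply is that little depends on this endpoint. It is exploratory, section 10.3.1 plans no statistical test, and the criterion for a positive result in section 5.1 is the Week 6 elbow MAS responder rate. This stands, and it limits how serious the point is.

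A reader might also infer that the open-label NRS is compared with Day 1, when only the elbow was rated, so that every non-elbow score is mismatched. The documents do not support that. The Day 1 definition in section 5.1 concerns the MAS: "at least 1 reduction on the MAS score from baseline (a measurement value before injection of Day 1". The protocol defines no NRS baseline. For the investigator CGI (section 9.1.1.4) the reference is V1 of each treatment phase, and choosing the NRS part at Visit 1 points the same way. The NRS baseline may properly be left to the SAP.

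**Conclusion.** The point holds in a limited form. As written, section 9.1.1.2 allows Visit 1 and later NRS scores of one open-label period to refer to different parts, and the exploratory change in NRS for that period is then not a change in any one part's pain. This follows from the text alone and rests on no numerical assumption.

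The size is unknown and the direction is not fixed. It would be tempting to conclude that the rule produces a spurious pain benefit for 400 units. That would require raters to move from the main painful part to a milder one, and nothing in the protocol prompts that. Choosing the worst part afresh at each visit would instead understate benefit.

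The blinded-period NRS and the primary endpoint are unaffected. The sentence should be corrected because the correction is cheap and a missed rating cannot be recovered later, but the trial's main conclusion does not depend on it.

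**What to change.** Replace the sentence in section 9.1.1.2 with wording to this effect: *the part named at Visit 1 of a treatment period is rated for pain at every visit of that period; it may differ only between treatment periods.* Then:

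- Record the rated part on the CRF at every NRS assessment, with an edit check against the part named at Visit 1 of that period.
- Where V5 or QRV is also the next period's V1 and the part changes, rate both: the old part to close the finished period and the new one to open the next.
- Compute open-label NRS change from that period's V1 score for the same part, and say so in the SAP.
- Flag and list any period already recorded with a switched part, and summarise with and without those periods. Simply dropping them would exclude data on a post-baseline event that may be related to outcome, and so could introduce selection.

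The cost is one protocol sentence, one CRF field with a check, a line in the SAP, and one extra pain question at shared visits where the part changes. Sample size and the primary analysis do not change.

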9.1.1.3. Disability Assessment Scale (DAS)

According to "2. SCHEDULE OF ACTIVITIES (SoA)" the investigator (or subinvestigator) will use the 4 disability assessment parameters presented in Table 7 and evaluate all of them based on the scale presented in Table 8. Before starting the study treatment, the investigator shall discuss with the subject, and select and evaluate 1 parameter agreed with the subject as the "main assessment parameter." The assessor should in principle remain unchanged throughout the study period. The main assessment parameter should also remain unchanged throughout the study period.

Table 7 Disability assessment parameters

	Content of assessment
Hygiene	The extent of maceration/ulceration and/or palmar infection, palm/hand cleanliness, ease of cleanliness, ease of nail trimming, and interference with hygiene-related disability in the subject's daily life
Pain	The intensity of pain/discomfort, and the interference that upper-limb pain-related disability has in the patient's daily life.
Dressing	The difficulty or ease for the subject in putting on the relevant clothing (e.g., shirts, jackets, gloves, etc.) and the interference that upper-limb dressing-related disability has in the patient's daily life.
Limb posture	The psychological and/or social interference that the disfigured upper limb has in the patient's daily life.

Table 8 Disability Assessment Scale

	Description
0: No functional disability	No functional disability
1: Mild disability	Noticeable but does not interfere significantly with normal activities
2: Moderate disability	Normal activities require increased effort and/or assistance.
3: Severe disability	Normal activities limited.

9.1.1.4. Clinical Global Impression of Change (CGI) assessed by an investigator

The investigator (or subinvestigator) will evaluate CGI according to "2. SCHEDULE OF ACTIVITIES (SoA)"; Changes in spasticity (Clinical Global Impression) from baseline (V1 in each treatment phase) will be evaluated by 9 grades as shown in Table 9.

The investigator shall also consider the subject's clinical symptoms and adverse events pertinent to the assessment of CGI. Also, the therapeutic effect of the product injected in the subject's fingers, wrist, and elbow should be taken into an account. The assessor should in principle remain unchanged throughout the study period.

Table 9 Clinical Global Impression of Change (CGI)

-4	Very much worsened
-3	Much worsened
-2	Moderately worsened
-1	Slightly worsened
0	Unchanged
+1	Slightly improved
+2	Moderately improved
+3	Much improved
+4	Very much improved

9.1.1.5. Clinical Global Impression of Change (CGI) assessed by a patient

According to "2. SCHEDULE OF ACTIVITIES (SoA)" the investigator (or subinvestigator) will use Table 9 to record subject-reported CGI. The investigator shall interview each subject on changes in spasticity from predose, and the subject will evaluate it using Table 9.

9.1.1.6. Time to patient-reported onset of spasticity symptom relief (Visit 2):

According to "2. SCHEDULE OF ACTIVITIES (SoA)" the investigator (or subinvestigator) will record the time to alleviation of spasticity reported by subjects. The investigator shall ask the subject whether the product was effective on the spasticity, and if the subject's response to the question is positive, ask him/her "how many days did it take for the therapeutic effect to appear after the current dose?" and record the number of days.

9.1.1.7. Patient-reported benefit of injection (Visits 3, 4, and 5)

According to "2. SCHEDULE OF ACTIVITIES (SoA)" the investigator (or subinvestigator) will record the efficacy of treatment reported by subjects. The investigator shall ask, "Was the product effective?" and the subject shall respond either by "Yes" or "No."

9.2. Adverse events

Definitions of adverse events and serious adverse events (SAE) are as specified in Appendix 4. The investigator or a person assigned by the investigator is responsible for detecting, recording, and reporting events that match the definitions of adverse events and SAEs, and also, responsible for follow-up investigations on SAEs, as well as events related to the study drug or this study, and events that resulted in treatment discontinuation or subject withdrawal (See section 8).

9.2.1. Period subject to collection of data related to adverse events and SAEs, and the frequency of such data collection

- All SAEs will be collected from the start of treatment until Final Visit at the time points specified in the SoA (Section 2).
- All AEs will be collected from the start of treatment until Final Visit at the time points specified in the SoA (Section 2).
- Medical occurrences that begin before the start of study treatment but after obtaining informed consent will be recorded on the Medical History/Current Medical Conditions section of the case report form (CRF) not the AE section.
- All SAEs will be recorded and reported to the sponsor or designee within 24 hours, as indicated in Appendix 4. The investigator will submit any updated SAE data to the sponsor within 24 hours of it being available.
- Investigators are not obligated to actively seek AEs or SAEs in former study participants. However, if the investigator learns of any SAE, including a death, at any time after a participant has been discharged from the study, and he/she considers the event to be reasonably related to the study treatment or study participation, the investigator must promptly notify the sponsor.
- The method of recording, evaluating, and assessing causality of AEs and SAEs and the procedures for completing and transmitting SAE reports are provided in Appendix 4.

